1.4 Regulatory background

On 7 July 2016 an application for a paediatric investigation plan (PIP) and deferral was submitted by the applicant Lupin (Europe) Ltd. And on 2 June 2017 the EMA granted a positive decision (P/0155/2017).

The applicant submitted on 26 June 2017 a Marketing Authorisation Application (MAA) for Namuscla through the centralised procedure. Subsequently, the PDCO was requested by the Agency to initiate a partial compliance procedure (EMEA-C1-002012-PIP01-16) which started on 18 July 2017 with a positive outcome on 15 August 2017.

On 18 October 2018, the Committee for Medicinal Products for Human Use (CHMP) adopted a positive opinion, recommending the granting of a marketing authorisation for the medicinal product Namuscla, intended for the treatment of myotonia in adults with certain hereditary muscle disorders (EMA/CHMP/650838/2018). The date of issue of the marketing authorisation valid throughout the European Union was 18th December 2018.

Several modifications to the initial PIP have been submitted and agreed and the current decision is P/0300/2023 for EMEA-002012-PIP01-16-M04. An additional modification (M05) was submitted in February 2024 and is ongoing. The changes in former modification M03 introduced the requirement for the current registry study, referred to as a prospective, long-term observational study (registry) of paediatric myotonic disorder patients from birth to less than 6 years of age who are treated with mexiletine. The study population was to include patients with myotonic disorders (DM1, DM2, and NDM) with a total of at least 10 paediatric subjects evaluable for the primary analysis with at least 4 patients in the birth to less than 6 in the in the 6 months to less than 6 years. Each participant must be followed for at least 2 years.

Based on epidemiological data, approximately 2 in 10,000 people are affected with myotonic disorders (which comprise the two main entities, myotonic dystrophies and non-dystrophic myotonias) in the EU. Consequently, mexiletine was granted orphan designation for "treatment of myotonic disorders" EU/3/14/1353 (EMA/OD/074/14). Namuscla was subsequently designated as an approved orphan medicinal product in the indication treatment of myotonic disorders after granting of the CHMP positive opinion. No protocol assistance procedure has ever been performed.

This trial will be conducted in compliance with the protocol, Declaration of Helsinki, Good Clinical Practice (GCP) and the applicable regulatory requirement(s).

There is a 2021 EMA guideline on registry-based studies (EMA/426390/2021, 2021) defined as an investigation of a research question using the data collection infrastructure or patient population of one or more patient registries. However, there is no equivalent guidance for a prospective patient registry for the currently proposed protocol. Which is an organised system that collects uniform data (clinical and other) to identify specified outcomes for a population defined by a particular disease, condition or exposure. Guidance exists on real world evidence as used to support regulatory filings, but only FDA has published clear guidance on this (FDA Center for Drug Evaluation and Research (CDER), 2023), whereas an ICH Concept Paper has also been recently published (EMA/CHMP/ICH/295401/2023, 2023).

The trial is considered as a non-intervention study:

- Assignment of patients is already decided in advance of the clinical trial protocol by the treating physician as part of normal clinical practice.
- The decision to prescribe a particular medicinal product is made prior to inclusion of the patient in the study.
- All diagnostic and monitoring procedures applied to the patients included in the study are applied as part of normal clinical practice.
- Mexiletine is currently authorised albeit not for paediatric patients. Nonetheless, use of mexiletine in this population is evidence-based and supported by published scientific evidence.

2 OBJECTIVES AND ENDPOINTS

2.1 Study Objectives

2.1.1 The Primary objectives

The objectives of this patient registry study are:

• To evaluate the safety and the efficacy (exploratory) of mexiletine for the treatment of myotonia in the paediatric population aged from birth to less than 6 years using real world data.

2.1.2 Secondary objectives

- To assess the suitability of mexiletine administration using available formulations including, where appropriate, capsules or opening and sprinkling contents in food or drink according to the child's age (from birth to less than 6 years) and ability to swallow.
- To understand how mexiletine is used by clinicians who have previously decided to use mexiletine for the treatment of myotonia in myotonic disorder patients, from birth to less than 6 years over a at least 2 years period, to establish risk:benefit conclusions.

3 STUDY DESIGN

3.1 Overall Study Design

This is an open-label, multi-centre, single arm, registry study to collect standard relevant clinical and epidemiological data during routine medical evaluation and treatment in paediatric patients with myotonic disorders who are being treated with mexiletine therapy according to the physician.

This study will be performed under routinary typical conditions without imposing any clinical practice or restrictions to the treating physician who prescribe and use mexiletine, or to the participants or caregivers and also without influencing in the usual clinical practice of patients with myotonias. With the exception of taking extra safety measures or performing tests, scales or questionnaires used as tools to protect the patient or to measure the outcomes of this study. Patients will not undergo any intervention whether for diagnostic, treatment or follow up purposes that are not usual in the clinical practice of their disease.

The participating centres will be selected based on their neurological specialisation and the treating physicians' expertise in the treatment of patients with myotonias.

3.2 Discussion of Study Design

Study inclusion screening time will be approximately 2 weeks.

Patients who meet the eligibility criteria will be enrolled in two cohorts by age groups although cohorts are not planned to necessarily enrol sequentially (cohort definition is to assure minimum requirements for meeting PIP agreements).

- Cohort 1 Infants and children aged between 6 months to less than 6 years.
- Cohort 2 Neonates and infants from birth to less than 6 months.

The overall treatment duration follow-up for each cohort will be at least 2 years.

Dosing and treatment administration in this registry study should be done as per the treating physician clinical practice.

Visits to the clinic are to occur according to routine site's clinical practice, or when applicable according to the treating practice physician.

An initial visit (i.e., screening equivalent that will also serve as baseline) will take place to ensure the patient currently complies with all participation. This visit will serve for the patient to enter the study.

The end of treatment (EOT) visit will be the first routine clinical practice visit after at least 2 years have been completed since the patient entered the study (baseline visit) or 2 weeks after the last mexiletine intake after 2 years of treatment (whichever occurs first).

After 24 months, no study specific visits and data collection are required and patients will be treated and followed up as per the investigator's site protocol.

The following data elements will be collected during this registry, as permitted by the clinical site normal clinical practice for patients with myotonic disorders and according to the patient's age, using as the example other myotonia registries (Lagrue *et al.*, 2019).

- Demographics
- Genetics: DM1, DM2 or NDM corresponding clinical forms
- Musculoskeletal manifestations (myotonia, facial hypotonia)
- Orthopaedic deformities (spine, feet or hands, orthoses, back brace, specialized followup, surgery)
- Cardiorespiratory signs (non-invasive ventilation, sleep disorders, ECG / left ventricular ejection fraction (LVEF), pacemaker/defibrillator)
- Ophthalmic and endocrinologic manifestations (cataract, diabetes, thyroid disorders)
- Psychomotor development disabilities
- Gastrointestinal (GI) disorders
- Patterns of mexiletine use including dose/ frequency.

Data will be entered at baseline upon patient enrolment and entered periodically thereafter for all routine clinical practice patient visits. For example, all laboratory values collected at routine clinical visits occurring between month 6 and month 12 of a patient's participation in the registry should be entered at the 12-month time point. All data will include the date each assessment was performed. Where available, additional retrospective data will be collected. Retrospective data will be focussed primarily on patterns of mexiletine use and dose adjustments as well as any efficacy assessments. Retrospective safety data will also be recorded, especially in relation to any AEs that affect dosing, SAEs or AESIs, but there will be no requirement to report any retrospective AEs prior to signing the informed consent. In cases where retrospective data are captured, this will be recorded from first mexiletine prescription up to the baseline visit or to the maximum age of eligibility for entering into the trial (that is, up to 6 years). For eligible patients who provide informed consent, data elements will be extracted from the information routinely recorded in the medical records and transcribed in to the electronic Case Report Forms (eCRF). Safety, treatment administration and efficacy assessments will be collected during the visits. AEs will be collected from the time informed consent is given to end of treatment.

No drug safety monitoring committee (DSMB) will be created.

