3.3 Selection of Study Population

3.3.1 Inclusion Criteria

- 1. Male or female patients from birth to less than 6 years
- 2. A genetically confirmed diagnosis of NDM or DM (DM1or DM2), as per the treating clinician.
- 3. Presence of clinical symptoms of myotonia (hand grip myotonia, myotonia in the leg muscles, any other myotonia symptoms) to be confirmed by the treating clinician.
- 4. Patients already receiving mexiletine treatment or who are clinically considered for mexiletine treatment as per the treating physician judgement.
- 5. No history of or significant cardiac abnormalities as determined by a cardiologist's assessment of the ECG and echocardiogram performed prior to enrolment in the study or as per the treating physician standard of care (NaMuscla SmPC, 2023)
- 6. No known history or signs and symptoms of any significant liver disorder as per treating physician.
- 7. No known clinically relevant abnormal laboratory investigations for haematology, biochemistry, and urinalysis values at screening (or based on values obtained within 3 months prior to screening in patient's medical record) that could affect the study objectives as judged by the treating physician.
- 8. Parent or legal guardian able to provide assent to study participation and to sign the written informed consent prior to study entry and perform any study-related activity.

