6 ENDPOINTS AND VARIABLES

6.1 **Primary Variables**

The endpoints to assess efficacy (exploratory) will be adapted to the patient's age and the corresponding tests they are able to perform. When feasible the following will apply in accordance with standard clinical practice:

- Muscle strength measured using the modified Medical Research Council (MRC) scale to evaluate neck flexors, shoulder abductors, elbow flexors and extensors, wrist extensors, finger flexors, hip flexors, knee flexors and extensors, posterior foot flexors and plantar flexors.
- Clinical Global Impression (CGI) Scores given to caregivers and assessed by the investigators
- Number and frequency of adverse events (AEs), serious adverse events (SAEs) and AE leading to treatment discontinuation, throughout the study while on treatment with mexiletine
- Incidence of adverse events of special interest (AESI)
- Description over time of efficacy outcomes obtained from clinically indicated tests as per the treating physician typical clinical practice and according to patient's age and cohort.
- Any changes in frequency, treatment interruptions of mexiletine.

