8.1.3 Recording and Collection of Adverse Events

It is the responsibility of the investigator to collect all AEs (both serious and non-serious) derived from spontaneous, unsolicited reports of patients, by observation and by routine open questions.

AE reporting will extend from date of informed consent until completion of the final visit (EOT). Any ongoing AE at end of study visit should be followed until the outcome is evident and resolved, clinically stabilized or a plausible explanation has been found.

Pre-existing diseases (before participating in the study) are not considered to be AEs, unless the disease worsens during the study period. Concomitant diseases prior to enrolment will be recorded in the eCRF.

Signs and symptoms clearly associated with the disease under study (including symptoms of disease progression) should be reported as AEs if they are newly emergent (i.e., findings not previously observed in the patients), or are determined by the investigator as severe or a worsening, or if the investigator considers deterioration of disease-related signs and symptoms to be caused directly by the study drug.

Abnormal laboratory values/ ECGs/ vital signs/ ophthalmic/ physical and systemic examination should be reported as AEs *only* if the Investigator considers the abnormality as clinically relevant or significant or believes that the abnormality should be reported as an AE.

Any dose (and associated symptoms) given to the patient that exceeds the dose prescribed to the patient has, at a minimum, to be recorded as a non-serious AE in the patient file and CRF/ eCRF. Any case of overdose leading to an AE or SAE should be reported to Medical Monitor according to reporting requirements. In case of an accidental overdose, the patient should be monitored by the Investigator for any adverse clinical events, as deemed necessary by the Investigator.

After completion of all visit assessments, the Investigator must document any AEs arising from these assessments. In case of an SAE, the Investigator must also complete an SAE report form and report it to safety contact, as described in Section 8.1.4.2 Relationship to the Study Drug.

All AEs will be recorded in case report form (eCRF) regardless of the causal relationship to the study drug.

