8.14 Safety Analysis

All summaries of adverse events will use only treatment emergent adverse event (TEAE) records.

In general, events will be described by counts and percentages.

Following information will be summarized for TEAEs.

- Overall Summary of TEAEs
- TEAEs by preferred term and System Organ Class (SOC)
- Treatment Related TEAEs by preferred term and SOC
- TEAEs by preferred term and SOC, Maximum Severity and Relationship
- Serious TEAEs by preferred term and SOC

• TEAEs leading to discontinuation of study drug by preferred term and SOC

Also, listing of all adverse events will be provided. The listing will include Adverse event number, description, preferred term, SOC, Start and End Date, Seriousness, Frequency of Occurrence, Severity, Action taken regarding study treatment, outcome, relationship to study treatment.

When collected laboratory and vital signs parameters will be summarised descriptively. Laboratory tests done at screening will be considered baseline.

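### Adverse events are collected systematically only from consent, and children already on mexiletine are pooled with new starters, so the planned percentages may understate the risk of starting treatment

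*Protocol*

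**What the plan says.** - **Who enters.** Protocol 3.3.1, criterion 4, admits "Patients already receiving mexiletine treatment or who are clinically considered for mexiletine treatment as per the treating physician judgement". Section 5.1 also provides for children previously prescribed the drug, so prior users are expected.
- **When AE collection starts.** Section 3.2: "AEs will be collected from the time informed consent is given to end of treatment". Section 8.1.3 gives the same window, from consent to the final visit.
- **Time on drug before consent.** Section 3.2: "Retrospective safety data will also be recorded, especially in relation to any AEs that affect dosing, SAEs or AESIs". The same sentence continues that "there will be no requirement to report any retrospective AEs prior to signing the informed consent". Retrospective data as a whole are collected only where available.
- **Primary variable.** Section 6.1 lists "Number and frequency of adverse events (AEs), serious adverse events (SAEs) and AE leading to treatment discontinuation".
- **Analysis.** Section 8.12 defines one Safety population, by a dose taken after consent. Section 8.14 restricts AE summaries to treatment-emergent events (TEAEs) and says "In general, events will be described by counts and percentages". The synopsis (Statistical Analysis) names two levels of presentation: all patients, and age cohort.
- **TEAE definition.** Section 8.1.1 ties a TEAE to at least one dose of study drug. It does not say whether this means the first dose ever or the first dose after consent.

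**The concern.** Safety is part of the primary objective, in an age group for which section 1.2 says safety has not been established. A new starter is observed from the first dose. A prior user is observed systematically only from some later point, having stayed on the drug long enough to be a current user at consent. The early weeks of treatment in that child are known only through whatever the chart holds.

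Selection adds to this. A child who stopped because of toxicity is unlikely to enter as a current user. Section 3.3.2 excludes ventricular and atrial tachyarrhythmia, heart block, hypersensitivity and seizure disorder. A child in whom such a condition arose on mexiletine before consent is therefore ineligible, while the same event in a new starter after consent is counted. Section 8.1.3 also treats disease present before participation as background unless it worsens. A drug-related condition already present at consent is then not an AE for a prior user, but would be one for a new starter.

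The pooled percentages could be read as the risk a child faces on starting mexiletine. In part they would describe children who had already tolerated it.

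**Working it through.** **1. The plan's own figure.** Section 8.8 gives at least 4 children in cohort 2 and at least 6 in cohort 1: 4 + 6 = 10, the stated minimum. The study is descriptive, so there is no power calculation to reproduce. The protocol does not say how many of the 10 will be prior users.

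**2. What differs between the groups.** Follow-up is at least 2 years from study entry for every child, so the planned observation window is of similar length. What differs is where it sits on the treatment timeline: from first dose for new starters, later for prior users.

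**3. Whether the age split removes the difference.** A cohort 2 child is under 6 months old at entry, so prior use is under 6 months. A cohort 1 child may have years of prior use. The age split therefore does not separate prior users from new starters, and it partly confounds age with time on drug.

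**4. Illustration on assumed values.** None of these inputs is in the protocol: early-onset AE risk p = 10% to 30%; k prior users among 10 children; m = 10 − k new starters; no early event of a prior user reaching the tables (worst case).

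- Chance of seeing at least one early event = 1 − (1 − p)^m
- Expected pooled percentage = p × m / 10
- One-sided 95% upper bound when no early event is seen in m children = 1 − 0.05^(1/m)

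| Prior users k | Observed from first dose m | Chance of ≥1 event, p = 10% / 20% / 30% | Expected pooled %, p = 20% | Upper bound if none seen |
|---|---|---|---|---|
| 0 | 10 | 65% / 89% / 97% | 20% | 26% |
| 5 | 5 | 41% / 67% / 83% | 10% | 45% |
| 7 | 3 | 27% / 49% / 66% | 6% | 63% |

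**5. Partial retrospective capture.** If a fraction c of prior users' early events were retrieved and counted, and prior users had the same early risk as new starters, the expected pooled percentage would be p × (m + c × k) / 10. With p = 20% and k = 5, c = 0 gives 10%, c = 0.5 gives 0.20 × 7.5 / 10 = 15%, and c = 1 gives 20%. Selection before consent would keep the figure below 20% even at c = 1.

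**6. When there is no bias.** With a constant hazard that is the same for all children, the expected number of events in the 2 years after consent is equal in both groups, and pooling does no harm.

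**The case against.** The strongest reply is that the early period is not ignored. Section 3.2 directs retrospective recording to the events that matter most, from the first prescription onward. The waiver concerns reporting, a word that section 8.1.4.2 uses for notification within 24 hours, so it may mean only that old events need no expedited notice. This stands in part: a reader might infer that early toxicity in prior users goes wholly unseen, and the text does not support that. But the retrospective data depend on availability, minor events are not a priority, and section 8.1.1 leaves open whether these events enter the TEAE tables.

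A second reply is that splits by prior use and exposure-adjusted rates belong in the statistical analysis plan, which is not shown. That plan may add them. The protocol, however, itself states the presentation as overall and by age cohort, so this is more than silence.

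Two stronger readings should be resisted.
- A reader might infer that AE frequencies must fall as the share of prior users rises, whatever the drug does. That requires early concentration of risk or loss of susceptible children, and the protocol gives no figure for either.
- A reader might take the share of total drug time that falls after consent as the size of the bias. Time before consent is not in the safety denominator, so that share does not measure it.

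Finally, prospective collection cannot begin before consent, and the listing of all AEs required by section 8.14 is informative with about 10 children. Both points are fair. They limit the remedy to presentation and definitions.

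**Conclusion.** The concern holds in a conditional form. As written, the plan pools children observed from first dose with children selected for having tolerated mexiletine, and it presents a primary safety variable without separating them. If risk is concentrated early, or susceptible children are lost before consent, the pooled percentages understate initiation risk.

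The amount cannot be derived from the protocol, because neither the share of prior users nor the timing of risk is given. It is nil if every child is a new starter. Under the worst-case assumptions above, with 5 of 10 prior users, a 20% early risk would be expected to appear as 10%. If no early event were seen, the upper bound would be 45% on the 5 children actually observed from first dose, against 26% if all 10 had been. The point merits correction because safety is a primary objective and the correction is cheap; it does not invalidate the registry.

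**What to change.** - **Section 8.14:** present the main TEAE, serious AE and discontinuation summaries separately for new starters (first dose at or after consent) and prior users, as well as overall, with on-study patient-years for each group. State that early-treatment risk is described from new starters only.
- **Data collection:** make the date of first mexiletine dose a required field. At present it is secured only where retrospective data happen to be captured. Show time since first dose in the AE listing.
- **Section 8.1.1:** state that the tabulated TEAEs are those with onset or worsening after consent while on drug. List retrospective events separately and do not add them to the tables.

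A grid of rates by interval since first dose is not advised: with about 10 children most cells would be empty or nearly so. The cost is protocol wording, one required field and a few extra tables, with no added visits or patients. The drawback is very small groups, so the separate percentages will be imprecise and should be read alongside the listing.
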